3.9.4.2 Partial seizures freedom

Criteria 1 and 2 (see Section 3.9.4.1) are the same as for all epileptic seizure freedom. However, criterion 3 is modified to only include partial seizures.

3. The subject did not report any partial seizures over the Treatment Period

Criterion 3: A subject meets criterion 3 if there are no records of partial seizures from Visit 4 up to Visit 7 in the Seizure Counts CRF module with either a partial seizure frequency count >0 or a reported partial seizure code with an unknown or missing seizure count.

3.9.5 Time to *n*th partial seizure

The evaluation of time to n^{th} partial seizure is based on the relative day of occurrence of the n^{th} partial seizure (n=1, 5, and 10) during the Treatment Period. Only seizure DRC data from the randomization up to and including the last visit of the Treatment Period will be considered. The algorithms described in Section 3.9.2 also apply to this analysis.

The time to n^{th} seizure will be calculated as the date of the n^{th} partial seizure minus the date of randomization plus 1 day for subjects who have at least n partial seizures in the Treatment Period. Subjects with fewer than n partial seizures during this period will be addressed as follows:

- Subjects who complete the Treatment Period will be analyzed as censored cases with date of censoring (ie, analyzed as non-events) based on the date of last dose of IMP during the Treatment Period.
- Subjects who discontinue due to lack of efficacy during the Treatment Period will be analyzed as having the nth seizure (i.e. as an event) on the date of last dose of IMP during the Treatment Period.
- Subjects who discontinue for reasons other than lack of efficacy during the Treatment Period will be analyzed as censored cases with date of censoring based on the date of last dose of IMP during the Treatment Period.

For those cases, time to censoring or time to event will be calculated as the date of last dose of IMP during the Treatment Period minus the date of randomization plus 1 day.

3.9.6

Dose mapping for total daily BRV dose

During the Treatment Period, subjects are to take 3 tablets twice per day (morning and evening) except for the first day where they will only take the evening dose, and the last day where they will only take the morning dose.

The 3 tablets will consist of: 2×50 mg BRV tablets and 1×25 mg PBO tablet for subjects randomized to the BRV 200mg treatment group; 1 × 25mg BRV tablet and 2 × 50mg PBO tablets for subjects randomized to the BRV 50mg treatment group; 2×50 mg PBO tablets and 1 × 25mg PBO tablet for subjects randomized to the PBO group, as shown in Table 3.1.

Table 3.1: Doses of individual BRV and PBO tablets during the Treatment Period

| | | Individua | l tablet co | ntents and | dose (mg) | |
|-----------------|--------|-----------|-------------|------------|-----------|--------|
| Treatment group | | Morning | | | Evening | |
| BRV 200mg/day | BRV 50 | BRV 50 | PBO 25 | BRV 50 | BRV 50 | PBO 25 |
| BRV 50mg/day | PBO 50 | PBO 50 | BRV 25 | PBO 50 | PBO 50 | BRV 25 |
| РВО | PBO 50 | PBO 50 | PBO 25 | PBO 50 | PBO 50 | PBO 25 |

During the Transition Period subjects are to take 2 tablets twice per day (morning and evening) except for the first day where they will only take the evening dose, and the last day where they will only take the morning dose. The 2 tablets will consist of: 1×50 mg BRV tablet and $1 \times$ 25mg BRV tablet for subjects randomized to the BRV 200mg treatment group; 1×25 mg BRV tablet and 1×50 mg PBO tablet for subjects randomized to the BRV 50 mg treatment group; 1×10^{-10} 50mg PBO tablet and 1×25 mg PBO tablet for subjects randomized to the PBO group, as shown in Table 3.2.

Table 3.2: Doses of individual BRV and PBO tablets during the Transition Period

| | Individua | l tablet co | ntents and | dose (mg) |
|-----------------|-----------|-------------|------------|-----------|
| Treatment group | Mor | ning | Eve | ning |
| BRV 200mg/day | BRV 50 | BRV 25 | BRV 50 | BRV 25 |
| BRV 50mg/day | PBO 50 | BRV 25 | PBO 50 | BRV 25 |
| РВО | PBO 50 | PBO 25 | PBO 50 | PBO 25 |

During the Down-Titration Period in weeks 1 to 3 subjects are to take 2 tablets twice per day (morning and evening) except for the first day where they will only take the evening dose, and the last day where they will only take the morning dose. In week 4 subjects will take 2 tablets in the morning only. The total dose of BRV will decrease each week, as shown in Table 3.3.

| RV and PBO tablets during the Down-Titration |
|--|
| |

| n, | | Individual tablet contents and dose (mg) | | | | |
|-----------------|------------------------|--|--------|---------|--------|--|
| Treatment group | | Morning | | Evening | | |
| 0 | BRV 200mg/day | | | | | |
| x his | BRV 150mg/day (Week1) | BRV 50 | BRV 25 | BRV 50 | BRV 25 | |
| \sim | BRV 100mg/day (Week 2) | BRV 50 | PBO 25 | BRV 50 | PBO 25 | |
| | BRV 50mg/day (Week 3) | PBO 50 | BRV 25 | PBO 50 | BRV 25 | |
| | BRV 25mg/day (Week4) | PBO 50 | BRV 25 | - | - | |

| | Individual tablet contents and dose (mg) | | | |
|----------------------|--|--------|--------|--------|
| Treatment group | Mor | ning | Eve | ning |
| BRV 50mg/day | | | | |
| BRV 25mg/day (Week1) | PBO 50 | BRV 25 | PBO 50 | PBO 25 |
| PBO (Week 2 & 3) | PBO 50 | PBO 25 | PBO 50 | PBO 25 |
| PBO (Week 4) | PBO 50 | PBO 25 | | _ |
| РВО | | | | |
| PBO (Week 1, 2 & 3) | PBO 50 | BRV 25 | PBO 50 | PBO 25 |
| PBO (Week 4) | PBO 50 | PBO 25 | | 0 |

In the drug dosing log CRF the daily total blinded dose (BRV + PBO) is recorded. The appendix Section 12.1 describes how to determine the daily BRV dose and number of tablets taken using the total blinded dose for each treatment group. It should be noted that when a subject is on 200mg BRV or 50mg BRV treatment and if subject takes less than the number of tablets per day they are supposed to take, it is unknown whether they missed an active or placebo treatment. It is assumed that the subject took the active treatment before PBO. For example, suppose a BRV 200mg subject used 3 tablets on a study day during the Treatment Period, and this day was not their first or last day during the Treatment Period, it would be assumed that the subject used the 3 × 50mg BRV tablets so would have a BRV quantity of 150mg BRV tablets.

If a subject on 200mg BRV or 50mg BRV treatment exceeds the number of tablets per day they are supposed to take, it is assumed they begin retaking the tablets for the same study day, and it is assumed that the subject took active treatment before PBO for the additional tablets. For example, suppose a BRV 200mg subject used 7 tablets on a study day during the Treatment Period, and this day was not their first or last day during the treatment period, it would be assumed that the subject used the 4×50 mg BRV tablets and 2 PBO tablets they were supposed to take on the study day, and an additional active treatment of 50mg so they would have a BRV quantity of 250mg BRV tablets.

In the circumstance the daily total blinded dose as recorded on the CRF exceeds the maximum nominal dose as described in the appendix Section 12.1, it is assumed the subject took the active treatment for all additional dosage. For example, suppose a BRV 200mg subject was recorded 275 mg/day total daily dose during the treatment period on the CRF (exceeding the maximum dose of 200 mg/day during the treatment period), it would be assumed the subject took active 200mg + 75 mg = 275 mg/day.

.10 Changes to protocol-defined analyses

Not applicable

S3.11

Consideration for COVID-19

A new COVID-19 CRF, to evaluate the impact of global pandemic was created and implemented to collect the information on impacted visit, impact category, and relationship to COVID-19.

The relationship to COVID-19 global pandemic will be assessed and captured in CRF form COVID-19 Impact: "Relationship to COVID-19" as: confirmed COVID-19 infection, suspected

COVID-19 infection, general circumstances around COVID-19 without infection or any other deviation from the protocol due to COVID-19.

Summary and listing (see Section 5.1.3) to describe the impact due to COVID-19 will be performed.

Summary and listing to describe the AE related to COVID-19 vaccination will be provided (see Section 10.2.1)

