3.2 General study level definitions

3.2.1 Analysis time points

3.2.1.1 **Relative day**

norization Relative day will be calculated as the current date minus the date of first dose of study drug for days prior to the date of first dose of study drug, and the current date minus the date of first dose of study drug plus 1 for days on or after the date of first dose of study drug and prior to or on the day of last study drug dose (eg, the day of first dose will be Day 1 and the day prior to first dose will be Day -1). For days after the last dose of study drug (including Open-Label Temporary Period), relative day will be calculated as the current date minus the date of last dose of study drug and will include a '+' to denote post-treatment days (eg, the day after the last dose will be Day +1). Relative day will not be calculated for partial dates.

3.2.2 **Study periods**

All measurements will be classified into study periods as follows

| | Baseline Period | From the date of Visit 1 prior to the date of Visit 3. |
|------|------------------------|--|
| | Treatment Period | From the date of Visit 3 until the day of Visit 7 in subjects who complete the Treatment Period; or EDV in subjects who discontinue treatment early prior to Visit 7. |
| | Ŏ | A subject is considered starting Treatment Period if the subject enters Visit 3 and is randomized. If a subject does not have a Visit 7 or EDV date, then either the date of the last scheduled or unscheduled visit during the Treatment Period or the date of last known dose of IMP during the Treatment Period, whichever is later, will define the end date of the Treatment Period. |
| | Down-Titration Period | From immediately after the last visit of the Treatment Period (Visit 7 or EDV) until Visit 8 for subjects who take any IMP during the Down-Titration Period. |
| ~ | Down-Titration Period | For subjects who enter the Down-Titration Period after the Transition Period without entering either LTFU study, MAP, or the Open-Label Temporary Period, it starts from immediately after the last visit of the Transition Period (Visit 8 Week 14). |
| THIS | Study Drug-Free Period | From immediately after the last visit of the Down-Titration Period until date of Safety Visit for subjects who enter the Down-Titration Period. |
| | Transition Period | From immediately after the last visit of the Treatment Period (Visit 7 or EDV) until Visit 8 for subjects who take any IMP |

| .3 End of treatm | nent value | |

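### Time to nth seizure counts events up to the last Treatment Period visit but censors event-free subjects at last dose, so the cut-off depends on the outcome for anyone off drug before that visit

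*SAP*

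**What the plan says.** **Events.** SAP 3.9.5 sets the window: "Only seizure DRC data from the randomization up to and including the last visit of the Treatment Period will be considered". An nth seizure is timed at its own date, counted from randomization, "plus 1 day for subjects who have at least n partial seizures in the Treatment Period". SAP 3.2.2 ends the Treatment Period at Visit 7, "or EDV in subjects who discontinue treatment early prior to Visit 7". With neither visit, the last visit in the period or the last known dose, "whichever is later, will define the end date of the Treatment Period".

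**Fewer than n seizures.** SAP 3.9.5 has three rules:

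- Completers: "Subjects who complete the Treatment Period will be analyzed as censored cases with date of censoring (ie, analyzed as non-events) based on the date". The date in question is that of the final dose in the period.
- Discontinuation for lack of efficacy: "analyzed as having the nth seizure (i.e. as an event) on the date of last dose of IMP".
- Discontinuation for any other reason: censored, with "date of censoring based on the date of last dose of IMP during the Treatment Period".

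A closing sentence repeats the last-dose date for all three. No rule stops event counting at last dose, and none moves censoring out to the last visit.

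**Analysis.** SAP 8.2.6 plans Kaplan-Meier medians and plots, and a proportional hazards model reporting p-values, hazard ratios and 95% confidence intervals. Under SAP Section 8, secondary tests use a nominal two-sided 0.05 level without multiplicity adjustment.

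**The concern.** The end of follow-up is set by one date for subjects who have the event and by another for those who do not. Where the dates differ, a subject belongs to the risk set in the gap only by having the nth seizure there. The numerator gains the gap events while the denominator loses the gap time of everyone who stayed event-free. Kaplan-Meier and Cox methods assume that leaving the risk set carries no information about whether the event follows. This rule breaks that assumption by construction.

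At stake is the accuracy of the medians, curves and hazard ratios for a listed secondary endpoint (n = 1, 5, 10). The primary analysis is not touched. For discontinuers, SAP 4.2 computes seizure frequency from diary data up to the last Treatment Period visit, so the two endpoints treat the same days differently and the SAP gives no reason.

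**Working it through.** The plan states no figure for this point, so the check is a reading of the rules followed by an illustration of size.

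**1. One subject under the written rules.** Drug stops on day 30 and the EDV is on day 40.

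| Course | Analysis time | Status | Days 31 to 40 |
|---|---|---|---|
| nth seizure on day 38 | 38 | event | at risk to day 38 |
| no nth seizure by day 40 | 30 | censored | discarded |

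A single cut-off would give 38 (event) and 40 (censored), or 30 (censored) in both cases.

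**2. Who can have a gap.**

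- Completers: essentially none. SAP 3.9.6 describes "the last day where they will only take the morning dose", so last dose and Visit 7 share a date.
- Discontinuers who take drug up to the EDV: none.
- Subjects whose drug stops before the visit: yes. Examples are an immediate stop under the liver criteria (Protocol 6.3.1) or an unprompted stop.
- Lack-of-efficacy discontinuers with fewer than n seizures: not censored, so outside this point.

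**3. Which n is exposed.** Inclusion criterion 9 requires at least 8 partial seizures in 8 weeks, which is 8/56 × 28 = 4 per 28 days. If that minimum rate continued, the expected wait would be 28/4 = 7 days for the first seizure, 5 × 7 = 35 for the fifth and 10 × 7 = 70 for the tenth. Few subjects are still event-free for n = 1 when they stop drug. Many may be for n = 10.

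**4. Size within one arm.** Assumptions, none from the documents: seizure rates gamma-distributed between subjects (mean 9 per 28 days, floor 2); last dose of discontinuers uniform over days 5 to 80; every discontinuer has the gap; none stops for lack of efficacy. Quantity: the crude event rate under the SAP rule divided by the rate with censoring at the last visit, minus 1. Ranges run over 5 to 20% discontinuing and gaps of 3 to 14 days.

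| n | Whole arm | Discontinuers only |
|---|---|---|
| 1 | 0.1 to 0.5% | about 1 to 3% |
| 5 | 0.2 to 1.8% | about 4 to 11% |
| 10 | 0.2 to 2.5% | about 5 to 18% |

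**5. Size between arms.** The shift in the rate ratio is the quotient of the two arms' inflation factors. For n = 10:

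- 5% vs 10% discontinuing, 7-day gap: 1.0072/1.0035 = 1.004
- 5% vs 10%, 14-day gap: 1.0124/1.0059 = 1.006
- 5% vs 20%, 14-day gap: 1.0254/1.0059 = 1.019
- Equal discontinuation and equal gaps: 1.000, because the factors cancel

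**6. Cox model under the null.** Assumptions: 148 per arm, lognormal rates with median 10 per 28 days and SD 0.8, n = 10. Result: the hazard ratio under the SAP rule divided by that under a matched window, 1500 replicates.

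| Discontinuing | Gap | Unadjusted | Adjusted for log seizure rate |
|---|---|---|---|
| 5% vs 10% | 7 days | 1.004 | 1.003 |
| 5% vs 10% | 14 days | 1.007 | 1.004 |
| 5% vs 5% | 14 days | 1.000 | not computed |

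If only 20% of discontinuers have a 14-day gap, the 5% vs 10% figure falls to 1.001. Harsher inputs give about 1.010 to 1.013 (15% discontinuing, 14 days) and 1.013 to 1.03 (20%, 21 days). The spread in the last pair is between simulation runs, one of only 60 replicates, so 1.03 is an upper indication.

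The SD of the log hazard ratio is about 0.12 to 0.14. The 1.007 case is therefore ln(1.007) = 0.0070, or 0.0070/0.14 = 5% to 0.0070/0.12 = 6% of one standard error.

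**The case against.** The strongest reply is that the gap hardly exists. Completers dose on the morning of Visit 7. The Protocol's treatment section applies down-titration to early discontinuers, and the schedule of assessments dispenses drug at the EDV and leads into the Down-Titration Period. A discontinuer who follows the plan is thus on drug when the Treatment Period ends. This stands, and it confines the point to subjects who stop beforehand. The rule is still wrong for those subjects, and no other section corrects it.

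A second reply is that the effect is negligible on a nominal secondary endpoint. The size is conceded. It bears on priority, not on whether the rule is coherent.

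A third is that an excess of gaps on brivaracetam would raise the brivaracetam hazard and so work against the drug. That is correct, but an excess on placebo would do the opposite.

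A fourth is that censoring at the EDV adds off-drug days, and that cutting both events and censoring at last dose would remove the mismatch equally well. This also stands. The two versions answer different questions, and either is coherent where the present mixture is not.

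**Conclusion.** The point holds in a narrow form. For a subject off drug before the last Treatment Period visit, and not discontinued for lack of efficacy, SAP 3.9.5 makes the end of follow-up depend on the outcome and slightly inflates that arm's hazard. With moderate assumed differences between arms the hazard ratio shift is about 0 to 1%, and slightly more only in extreme scenarios. It is close to nil for n = 1 and largest for n = 10. These sizes rest on assumed seizure rates, discontinuation and gap lengths, since the documents give none. The priority is low: no primary conclusion is at risk.

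Two stronger readings are tempting, and the documents support neither:

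- A reader might infer that the 200 mg/day arm is the one penalised. SAP 4.2 reports few dropouts in earlier similar brivaracetam studies and no clear relation to dose, overall or for adverse events. Protocol 2.4 describes discontinuation as low and similar to placebo. Without a difference in gaps between arms, the ratio does not move.
- A reader might infer that the error always runs one way. When neither Visit 7 nor EDV exists, last dose can fall after the last visit. Diary data stop at that visit, so an event-free subject would be censored beyond the diary window, which lowers the hazard.

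**What to change.** Use one cut-off for events and censoring. In SAP 3.9.5, censor subjects with fewer than n partial seizures who complete the Treatment Period, or who discontinue for a reason other than lack of efficacy, at the last day with diary data in the Treatment Period. Amend the closing sentence so that the last-dose date applies only to the imputed lack-of-efficacy events. This matches the data window in SAP 4.2 and also prevents censoring beyond the diary when last dose follows the last visit.

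The cost is one sentence and one derivation line, using diary data already collected. The downside is small: a few off-drug days enter the risk time. A sensitivity analysis that cuts both events and censoring at last dose would give the on-treatment answer. If treatment codes have already been released, report the change as a labelled sensitivity analysis.

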### 7 STUDY TREATMENT(S)

### Description of investigational medicinal product(s) 7.1

Oral film-coated tablets of BRV 25mg, BRV 50mg, and matching PBO tablets will be used in

After an 8-Week Baseline Period and once the subject has fulfilled the eligibility criteria, he/she will be randomized to 50mg/day group, 200mg/day group or PBO group, and enter the double-blind Treatment Period (Visit 3 to Visit 7).

During the Treatment Period, subjects will be treated with BRV 50mg/day, BRV 200mg/day, or the matching PBO tablets in a double-blinded manner. Study medication should be given as 2 equally divided doses administered twice daily except the last week of down-titration. Study medication in the last week of down-titration is given only in the morning. The first intake of newly dispensed study medication should occur in the evening of each visit. Subjects should take IMP according to instructions provided by Investigator.

At the end of the Treatment Period (Visit 7), the subjects entering into the LTFU study or MAP will enter the Transition Period or the subjects not entering into the LTFU study or MAP will enter the Down-Titration Period followed by a Study Drug-Free Period.

The Transition Period (2 weeks) will consist of the following:

- For subjects randomized to BRV 50mg/day group or PBO group, keep same dose as Treatment Period during the Transition Period.
- For subjects randomized to BRV 200mg/day group, the Transition Period will consist of the • following: 2 weeks at BRV 150mg/day.

The Down-Titration Period (4 weeks) will consist of the following:

- For subjects randomized to PBO group, keep PBO during the Down-Titration Period.
- For subjects randomized to BRV 50mg/day group, the Down-Titration Period will consist of the following: 1 week at BRV 25mg/day followed by 3 weeks at PBO.
- For subjects randomized to BRV 200mg/day group, the Down-Titration Period will consist of the following: I week at BRV 150mg/day, 1 week at BRV 100mg/day, 1 week at BRV 50mg/day, followed by 1 week at BRV 25mg/day.

The down-titration procedure needs to be applied in case of early discontinuation or completion without conversion to the LTFU study or MAP.

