12.1 Actual BRV dose conversion table

Table 12.1: Conversion from blinded daily dose to unblinded BRV daily dose

| UCB Statistical Analysis P | lan Bi | rivarace | tam | | | | | | | jj | xx A | ug 2022 EP0083 |
|-------------------------------|--|----------|--------|-------------|--------|--------|-----|-----|------|-----|------|-------------------|
| | PPENDICES | | | | | | | | nori | | | |
| | ctual BRV dose conversion table onversion from blinded daily dose to ur | nblind | led BF | RV da | ily do | se | ~0 | 30 | 0 | | | |
| | | | Blin | ded No | ominal | Dose (| | | | | | |
| Treatment group | Period or Visit | 0 | 25 | 50 | 75 | 100 | 125 | 150 | 175 | 200 | 225 | 250 |
| 200mg/day | Start day of Treatment Period | 0 | 0 | 50 | 50 | 100 | 100 | | | | | |
| | Treatment Period (except first and last dates) | 0 | 0 | 50 | 50 | 100 | 100 | 150 | 150 | 200 | 200 | 200 |
| | Day of end Treatment and start Transition | 0 | 25 | 50 | 75 | 100 | 125 | 150 | 175 | 175 | | |
| | Transition Period (except first and last dates) | 0 | 25 | 50 | 75 | 100 | 125 | 150 | | | | |
| | Last day of Transition Period | 0 | 25 | 50 C | 75 | | | | | | | |
| 50mg/day | Start day of Treatment Period | 0 | 25 | 0 | 25 | 0 | 25 | | | | | |
| | Treatment Period (except first and last dates) | 0 | 25 | 50 | 25 | 50 | 25 | 50 | 25 | 50 | 25 | 50 |
| | Day of end Treatment and start Transition | 0 | 25 | 50 | 25 | 50 | 25 | 50 | 25 | 50 | | |
| | Transition Period | -0 | 25 | 50 | 25 | 50 | 25 | 50 | | | | |
| | Last day of Transition Period | 0 | 25 | 0 | 25 | | | | | | | |
| РВО | Start day of Treatment Period | 0 | 0 | 0 | 0 | 0 | 0 | | | | | |
| | Treatment Period (except first and last dates) | 0 | 0 | 0 | 0 | 0 | 0 | 0 | 0 | 0 | 0 | 0 |
| | Day of end Treatment and start Transition | 0 | 0 | 0 | 0 | 0 | 0 | 0 | 0 | 0 | | |
| | Transition Period (except first and last dates) | 0 | 0 | 0 | 0 | 0 | 0 | 0 | | | | |
| | Last day of Transition Period | 0 | 0 | 0 | 0 | | | | | | | |

his locul app Note: Figures in italics indicate that there are two theoretically possible doses, of which the higher one is selected.

Confidential

12.2 **PCST** criteria

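### One placebo row of SAP Table 3.3 lists a BRV 25 tablet for down-titration weeks 1 to 3, contradicting its own label and Protocol 7.2, and Table 12.1 has no down-titration rows to override it

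*SAP*

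**What the plan says.** Protocol Section 7.2, on the placebo arm: "For subjects randomized to PBO group, keep PBO during the Down-Titration Period".

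SAP Section 3.9.6 gives tablet contents by arm and period. In Table 3.3 (Down-Titration Period), the placebo block has two rows, one for weeks 1 to 3 and one for week 4. The first begins "PBO (Week 1, 2 & 3) | PBO 50 | BRV 25" and in full reads: "PBO (Week 1, 2 & 3) | PBO 50 | BRV 25 | PBO 50 | PBO 25". The columns are two morning tablets followed by two evening tablets.

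Two rows of the BRV 50 mg/day block serve as comparisons:

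- Week 1, an active week: "BRV 25mg/day (Week1) | PBO 50 | BRV 25 | PBO 50 | PBO 25"
- Weeks 2 and 3, all placebo: "PBO (Week 2 & 3) | PBO 50 | PBO 25 | PBO 50 | PBO 25"

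On deriving the actual daily dose, Section 3.9.6 says: "The appendix Section 12.1 describes how to determine the daily BRV dose and number of tablets taken". The table in that appendix is titled "Conversion from blinded daily dose to unblinded BRV daily dose". Its rows cover the Treatment Period, the Transition Period and their boundary days. It has none for the Down-Titration Period.

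SAP Section 3.10 records no changes to the protocol-defined analyses.

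**The concern.** The weeks 1 to 3 placebo row conflicts with its own label and with the protocol. Its four cells are identical to the BRV 50 mg/day week 1 row, which suggests a copying slip, though the documents do not say how it arose.

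The row sits in a dose-mapping specification, not in background text. Table 12.1, which should settle the actual dose, does not cover down-titration. A programmer who needs a daily BRV dose in that period therefore has only Table 3.3 to work from. Read literally, it credits control-arm subjects with active drug.

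Two outputs could carry that error:

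- SAP Section 3.6 says that safety is, in general, analysed by the actual dose.
- The discontinuation listing in SAP Section 5.1.1 shows the dose at which a subject stopped and the days on that dose.

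**Working it through.** **Inputs.** Tablet contents come from SAP Table 3.3. The placebo regimen comes from Protocol 7.2. The half-day convention comes from SAP 3.9.6: the first day of the period is evening only.

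**Step 1. Does each row of Table 3.3 sum to its label?** BRV dose = sum of the BRV tablets in the row. Blinded dose = sum of all tablets in the row.

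| Arm and week | Labelled BRV, mg/day | BRV tablets, mg | BRV sum | Blinded sum | Tablets/day |
|---|---|---|---|---|---|
| BRV 200, week 1 | 150 | 50+25+50+25 | 150 | 150 | 4 |
| BRV 200, week 2 | 100 | 50+50 | 100 | 150 | 4 |
| BRV 200, week 3 | 50 | 25+25 | 50 | 150 | 4 |
| BRV 200, week 4 | 25 | 25 | 25 | 75 | 2 |
| BRV 50, week 1 | 25 | 25 | 25 | 150 | 4 |
| BRV 50, weeks 2–3 | 0 | none | 0 | 150 | 4 |
| BRV 50, week 4 | 0 | none | 0 | 75 | 2 |
| **PBO, weeks 1–3** | **0** | **25** | **25** | 150 | 4 |
| PBO, week 4 | 0 | none | 0 | 75 | 2 |

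Eight of the nine rows agree with their labels. The placebo row for weeks 1 to 3 does not.

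**Step 2. Amount credited if the row is applied literally.** The BRV cell is a morning tablet. Three weeks is 21 days. With an evening-only first day there are 21 − 1 = 20 mornings, so 25 × 20 = 500 mg. Counting through to the following morning gives 21 mornings, so 25 × 21 = 525 mg.

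**Step 3. Would the tablet count or blinded dose reveal the conflict?** No. A row of placebo tablets only, such as the BRV 50 row for weeks 2 and 3, has the same blinded total (50+25+50+25 = 150 mg) and the same four tablets a day. Only the active content differs.

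**Step 4. Which outputs use that content?**

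- Primary efficacy: planned treatment and the Treatment Period (SAP 3.6, 8.1). Not affected.
- Compliance: SAP Section 7 uses Table 3.3 for tablets per day only, which is 4 either way. Not affected.
- Exposure duration: first and last dose dates (SAP 10.1). Not affected.
- PK: the last dosage amount recorded on its own CRF form (SAP 9.1), with Visit 8 samples only in the Transition Period (Protocol Table 5–1). Not affected.
- TEAEs by study period: classified by period (SAP 10.2, 3.2.2), not by tablet content. The period assignment is not affected.
- Derived actual dose in down-titration, and any safety grouping that uses it (SAP 3.6): at risk.
- Discontinuation listing of dose and days on dose (SAP 5.1.1): at risk for a placebo subject who stops during down-titration.

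**The case against.** The strongest reply is that the SAP never instructs anyone to derive BRV dose from this cell. Derivation is referred to Table 12.1, where every placebo entry is 0, and the compliance rule takes only tablet counts from Table 3.3. SAP 3.6 opens by basing all analyses on the randomized group, as does Protocol 13.1, and the actual-dose rule for safety is qualified as general. Safety summaries show the randomized arms and combined BRV, with no 25 mg/day column into which a placebo subject could move. A programmer might also trust the row's placebo label over the cell.

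Much of this stands, and it limits the consequence. It does not remove the contradiction, and the zeros in Table 12.1 stop at the Transition Period. For down-titration, the wrong or unreconciled cell is in the only key available.

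A second reply is that the tables were read from PDF: the caption of Table 3.3 is truncated and stray characters appear nearby. A reading fault cannot be wholly excluded, but the row itself is complete and matches another row cell for cell. The cell should be confirmed in the signed SAP.

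A reader might infer three stronger things, none of which the documents support:

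- That placebo subjects were given BRV. Table 3.3 is an analysis specification, and nothing shows what was packaged or dispensed.
- That an assessment of withdrawal effects is compromised. Neither document gives the Down-Titration Period that purpose or plans such an analysis.
- That 148 subjects are affected. That is the planned analysable number per arm. The documents do not state how many placebo subjects enter down-titration, and those going to LTFU or MAP normally do not.

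**Conclusion.** The contradiction holds: one row of SAP Table 3.3 disagrees with its own label and with Protocol 7.2, by 25 mg/day of BRV. The missing Down-Titration rows in Table 12.1 leave nothing in the SAP to resolve it.

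The consequence is conditional and narrow. If down-titration dose is derived literally from Table 3.3, each placebo subject who completes weeks 1 to 3 is credited with 500 to 525 mg, assuming full intake and 20 to 21 mornings. The exposed outputs are the derived actual dose, to the extent that safety analyses use it, and the discontinuation listing. The primary result does not depend on this row. It should still be corrected, because it could put a false record of active exposure in the control arm.

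**What to change.** Before unblinding:

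1. Confirm the cell in the signed SAP.
2. Reconcile the weeks 1 to 3 placebo row of Table 3.3 with Protocol 7.2 and with the packaging list, correct whichever document is in error, and record the outcome.
3. Add Down-Titration rows to Table 12.1 for all three arms, including the boundary days as is already done for the Transition Period, so that they match the reconciled Table 3.3.
4. Check that the program deriving daily BRV dose reads the reconciled table.

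The cost is one reconciled table cell, a short extension of Table 12.1 and one check against the packaging list. No analysis method or sample size changes.
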